6.1.2 SELECTION OF DOSES IN THE STUDY

AZR-MD-001 1.0% ointment/semi-solid drug has been selected for evaluation in this study.

6.1.3 DOSING AND ADMINISTRATION

The study medication will be self-administered by the patient (or administered by a caregiver) at home in the evening.

Patients (or a caregiver) will apply a dose of approximately 3.5mm (0.14inch, 4mg) using a dosing aid supplied by Azura Ophthalmics. Patients will then use their washed index finger to apply the drug to the tarsus of the lower lid of both eyes in the evening just before bedtime. They will be instructed to press the ointment strip against their index finger to leave a thin and uniform ointment layer over the finger. The patient will then blink several times to transfer a portion of the drug from the lower eyelid to the upper eyelid (see the Dosing Instruction Sheet for more detail).

During the double-masked treatment period, each patient (or caregiver) must apply 1 application of the vehicle or active drug twice weekly in the evening to the tarsus of the lower lid of both eyes.

Multi-dose tubes of the masked study medication are each to be used for only 30 days to both eyes. The patient should be instructed to place the used tube in the used tube bag after use and should return used and unused tubes at the next study visit.

PREPARATION/HANDLING/STORAGE/ ACCOUNTABILITY

6.1.4 ACQUISITION AND ACCOUNTABILITY

Subjects will be instructed on proper instillation and storage of study drug at the end of the baseline (day 0), 2 weeks, 4 weeks and 6 weeks visits, will be given written instructions and may also watch an instructional video. The used and unused study drug tubes will be collected at each visit from baseline up to and including month 3 to assess dosing. Dosing compliance will be based off of the used and unused tube count. If the subject is less than 80% or more than 125% compliant with dosing based on the expected number of used tubes, then the subject will be deemed non-compliant and a deviation should be recorded.

6.1.5 FORMULATION, APPEARANCE, PACKAGING, AND LABELING

The study packaging will be performed by PCI Pharma Services (PCI). All packaging and labeling operations will be performed according to Good Manufacturing Practice for Medicinal Products and the relevant regulatory requirements.

Details of packaging and labeling are in final study documentation provided by PCI Pharma Services.

6.1.6 PRODUCT STORAGE AND STABILITY

The study medication must be stored in a secure area accessible only to the investigator and his/her designees. The study medication will be administered only to patients entered into the clinical study, in accordance with the conditions specified in this protocol.

The study medication is to only be prescribed by the principal investigator or his/her named sub-investigator(s), and is to only be used in accordance with this protocol. The study medication must only be distributed to patients properly qualified under this protocol to receive study medication.

The investigator must keep an accurate accounting of the study medication received from the supplier. This includes the amount of study medication dispensed to patients, amount of study medication returned to the investigator by the patients, and the amount returned or disposed upon the completion of the study. A detailed inventory must be completed for the study medication.

All study medication will be returned to Azura Ophthalmics or their designee or destroyed at the study site. The return or disposal of study medication will be specified in writing. AZR-MD-001 is to be refrigerated between 2 – 8°C until opened and protected from light. Maintenance of a temperature log (manual or automated) is required at the clinical site.

6.1.7 PREPARATION

Patients should let the study tube equilibrate at room temperature below 25°C for up to 15 minutes before dosing. Patients will use the study medication directly from the dose container in accordance with the protocol and should return the dose container to refrigeration between 2 – 8°C following successful dosing. For the next day of dosing, this process should be repeated. This in use pattern should continue for 30 days at which time the dose container should be used for a final day of dosing and then set aside for return to study investigator.

6.2 MEASURES TO MINIMIZE BIAS: RANDOMIZATION AND BLINDING

Site personnel conducting efficacy and safety measures will be masked to the treatment assignment for the 3 month treatment period.

Screening numbers will be assigned sequentially by site. At the end of the baseline visit, patients will be given a sequential randomization number which corresponds to a specific medication kit number(s) and type in the randomization log. Designated site personnel will report a medication kit number to use for each patient corresponding to the randomization number and will be responsible for monitoring and documenting patient compliance with dosing at each visit. The individual dispensing drug and monitoring compliance will not be the same person who conducts efficacy or safety measures for a given patient.

Additionally, site personnel will observe patients applying ointment from a tube labelled “Vaseline” at the baseline visit, and will have access to instructional dosing videos.

6.3 CONCOMITANT THERAPY

Patients must have discontinued and be willing to remain off all other ophthalmic preparations including artificial tears during the study (except those prescribed for use as part of the study).

6.3.1 RESCUE MEDICINE

In the event that rescue medication is required for worsening signs or symptoms of MGD or dry eye disease during the course of the study, patients will be provided an appropriate rescue regimen by the investigator/treating clinician, which may include ophthalmic corticosteroid preparations.

7 STUDY INTERVENTION DISCONTINUATION AND PARTICIPANT DISCONTINUATION/WITHDRAWAL

7.1 DISCONTINUATION OF STUDY INTERVENTION

Patients can voluntarily withdraw from the study at any time. The investigator can withdraw a patient from the study at any time for any reason. Additionally, patients can be discontinued from the study by an investigator if any of the following criteria are met:

- patient develops (or had an exacerbation of) any medical condition that, in the opinion of the investigator, would have put the patient at an unacceptable medical risk or compromised the patient’s ability to participate in the study
- patient is unwilling or unable to continue to comply with study procedures
- patient becomes pregnant

The study can be stopped at the study site(s) at any time by the site investigator(s). Azura Ophthalmics can also stop the study (and/or the study site[s]) with appropriate notification.

If a patient discontinues participation in the study early, every attempt must be made to complete the exit procedures.

7.2 PARTICIPANT DISCONTINUATION/WITHDRAWAL FROM THE STUDY

The investigator and Azura Ophthalmics have the right to withdraw a patient from the study at any time for any reason. When possible, the decision to withdraw a patient from the study should be discussed with the investigator.

Azura Ophthalmics may recommend the site withdraw a participant for the following reasons:

- i. Patient Safety: New data/findings plus a DRC decision from ongoing study AZ201801 indicates it is unsafe to continue patients in that study at a dose and frequency being used in the current study;
- ii. Manufacturing: Any problem identified with clinical supplies that may require stopping of dosing;
- iii. Negligence: A general right to stop a study in the event of overt negligence by either party.

Patients who are withdrawn early from the study should have early exit visit procedures completed at the time of withdrawal, or at their next scheduled visit, whenever possible.

7.3 LOST TO FOLLOW-UP

A patient will be considered lost to follow-up if he or she fails to return for 2 consecutive scheduled visits and is unable to be contacted by the study site staff.

The following actions must be taken if a participant fails to return to the clinic for a required study visit:

- The site will attempt to contact the participant and reschedule the missed visit within the specified visit window (see Table 1.3) and counsel the patient on the importance of maintaining the assigned visit schedule and ascertain if the participant wishes to and/or should continue in the study.
- Before a patient is deemed lost to follow-up, the investigator or designee will make every effort to regain contact with the participant (where possible, 3 telephone calls and, if necessary, a certified letter to the patient's last known mailing address or local equivalent methods). These contact attempts should be documented in the patient's medical record or study file.
- Should the patient continue to be unreachable, he or she will be considered to have withdrawn from the study with a primary reason of lost to follow-up.

8 STUDY ASSESSMENTS AND PROCEDURES

8.1 SAFETY AND OTHER ASSESSMENTS

8.1.1 SAFETY MEASURES

The following safety measures will be examined:

- adverse events (ocular and nonocular)
- study medication tolerability as measured by the Ocular Comfort Questionnaire
- best-corrected visual acuity (BCVA)
- slit-lamp biomicroscopy
- intraocular pressure (IOP)
- ophthalmoscopy

8.2 ADVERSE EVENTS AND SERIOUS ADVERSE EVENTS

Adverse events occurring during the study will be recorded on an adverse event form. If adverse events occur, the first concern will be the safety of the study participants.

All adverse events that are drug-related and unexpected (not listed as treatment-related in the current Investigator's Brochure) must be reported to the governing Institutional Review Board/Independent Ethics Committee (IRB/IEC) as required by the IRB/IEC, local regulations, and the governing health authorities. Any adverse event that is marked 'ongoing' at the exit visit must be followed-up as appropriate.

8.2.1 DEFINITION OF ADVERSE EVENTS (AE)

An AE is defined as any untoward medical occurrence in a clinical study subject administered a medicinal product which does not necessarily have a causal relationship with this treatment. An AE can therefore be any unfavorable and unintended sign (including an abnormal laboratory finding), symptom, or disease temporally associated with the use of a medicinal (investigational) product, whether or not it is related to the medicinal (investigational) product. This includes an exacerbation of pre-existing conditions or events, intercurrent illnesses, drug interaction or the significant worsening of the indication under investigation that is not recorded elsewhere in the

source under specific efficacy assessments. Anticipated fluctuations of pre-existing conditions, including the disease under study that do not represent a clinically significant exacerbation or worsening need not be considered AEs.

It is the responsibility of the investigator to document all AEs that occur during the study. AEs will be elicited by asking the subject a nonleading question, for example, "Have you experienced any new or changed symptoms since we last asked/since your last visit?". AEs should be reported on the appropriate source page.

Some illustrate examples follow to help understand the difference between events meeting the definition of an AE and those that don't.

Events meeting AE definition include:

- Any abnormal safety assessments (e.g., vital signs), including those that worsen from baseline, and felt to be clinically significant in the medical and scientific judgement of the investigator.
- Exacerbation of a chronic or intermittent pre-existing condition including either an increase in frequency and/or intensity of the condition.
- New conditions detected or diagnosed after study treatment administration even though it may have been present prior to the start of the study.
- Signs, symptoms, or the clinical sequelae of a suspected interaction.
- Signs, symptoms, or the clinical sequelae of a suspected overdose of either study treatment or a concomitant medication (overdose per se will not be reported as an AE/SAE unless this is an intentional overdose taken with possible suicidal/self-harming intent. This should be reported regardless of sequelae).
- "Lack of efficacy" or "failure of expected pharmacological action" per se will not be reported as an AE or SAE. However, the signs and symptoms and/or clinical sequelae resulting from lack of efficacy will be reported if they fulfil the definition of an AE or SAE.

Events NOT meeting definition of an AE include:

- Any clinically significant abnormal laboratory findings or other abnormal safety assessments which are associated with the underlying disease, unless judged by the investigator to be more severe than expected for the subject's condition.

- The disease/disorder being studied or expected progression, signs, or symptoms of the disease/disorder being studied, unless more severe than expected for the subject's condition.
- Medical or surgical procedure (e.g., endoscopy, appendectomy): the condition that leads to the procedure is an AE.
- Situations where an untoward medical occurrence did not occur (social and/or convenience admission to a hospital).
- Anticipated day-to-day fluctuations of pre-existing disease(s) or condition(s) present or detected at the start of the study that do not worsen.

8.2.2 DEFINITION OF SERIOUS ADVERSE EVENTS (SAE)

If an event is not an AE per the definition above, then it cannot be an SAE even if serious conditions are met (e.g., hospitalization for signs/symptoms of the disease under study, death due to progression of disease, etc).

An SAE is any untoward medical occurrence or effect that, at any dose,

- Results in death.
- Is life-threatening (an AE is life-threatening if the subject was at immediate risk of death from the event as it occurred, i.e., it does not include a reaction that might have caused death if it had occurred in a more serious form).
- Requires or prolongs inpatient hospitalization. (Complications occurring during hospitalization are AEs and are SAEs if they cause prolongation of the current hospitalization. Hospitalization for elective treatment of a pre-existing non-worsening condition is not, however, considered an AE. The details of such hospitalizations must be recorded on the medical history or physical examination page of the source).
- Results in persistent or significant disability/incapacity. (An AE is incapacitating or disabling if it results in a substantial and/or permanent disruption of the subject's ability to carry out normal life functions).
- Results in a congenital anomaly/birth defect.

In addition, medical and scientific judgement is required to decide if prompt notification is required in situations other than those defined for SAEs above. This may include any event that the investigator regards as serious that did not strictly meet the criteria above but may have jeopardized the subject or required intervention to prevent one of the outcomes listed above, or that would

suggest any significant hazard, contraindication, side effect, or precaution that may be associated with the use of the investigational product.

8.2.2.1 REPORTING OF SERIOUS ADVERSE EVENTS

Any SAE must be reported by the investigator if it occurs during the clinical study within 24 hours of the investigator's or site's knowledge of the event, whether or not the SAE is considered to be related to the investigational product. An SAE report consists of the SAE form, the AE form medical history and the concomitant medication form. SAEs will be reported to Azura Ophthalmics, the Human Research Ethics Committee and any other relevant approving authorities.

The site investigator will handle the SAE and ensure appropriate review and onward reporting to the Sponsor, with oversight of reporting to the ethics committees and competent authority as per local regulatory requirements:

For medical emergencies contact the medical monitor: [name]

[contact]

E-Mail: [contact]

The investigator should not wait to receive additional information to document fully the event before notification of a SAE, though additional information may be requested. Where applicable, information from relevant laboratory results, hospital case records, and autopsy reports should be obtained.

Instances of death, congenital abnormality, or an event that is of such clinical concern as to influence the overall assessment of safety, if brought to the attention of the investigator at any time after cessation of study drug administration and linked by the investigator to this study, should be reported to Azura Ophthalmics.

UNSW will promptly notify all relevant investigators and the regulatory authorities of findings that could adversely affect the safety of subjects, impact on the conduct of the study or alter the independent ethics committee (IEC)/institutional review board (IRB) approval/favorable opinion of the study.

Details of the procedures to be followed if a pregnancy occurs are provided in Section 8.3.7.

8.2.3 CLASSIFICATION OF AN ADVERSE EVENT

8.2.3.1 SEVERITY OF EVENT

A clinical determination will be made of the intensity of an adverse event. The severity assessment for a clinical adverse event must be completed using the following definitions as guidelines:

| | |
|----------|---|
| Mild | Awareness of sign or symptom, but easily tolerated |
| Moderate | Discomfort enough to cause interference with usual activity |
| Severe | Incapacitating with inability to work or do usual activity |

8.2.3.2 RELATIONSHIP TO STUDY INTERVENTION

A determination will be made of the relationship (if any) between an adverse event and the study drug or study procedure, as applicable. A causal relationship is present if a determination is made that there is a reasonable possibility that the adverse event may have been caused by the drug or study procedure. Causality should be assessed using the following categories:

- Unrelated: Clinical event with an incompatible time relationship to study drug administration, and that could be explained by underlying disease or other drugs or chemicals or is incontrovertibly not related to the study drug.
- Unlikely: Clinical event whose time relationship to study drug administration makes a causal connection improbable, but that could plausibly be explained by underlying disease or other drugs or chemicals.
- Possible: Clinical event with a reasonable time relationship to study drug administration, but that could also be explained by concurrent disease or other drugs or chemicals.
- Probable: Clinical event with a reasonable time relationship to study drug administration, and is unlikely to be attributed to concurrent disease or other drugs or chemicals.
- Very Likely/Certain: Clinical event with plausible time relationship to study drug administration, and that cannot be explained by concurrent disease or other drugs or chemicals.

8.2.3.3 ACTION TAKEN

The investigator will describe the action taken in the appropriate source document, as follows:

- None
- Study drug stopped
- Study drug temporarily interrupted
- Concomitant medication
- Other, specify.

8.2.4 TIME PERIOD & FREQUENCY FOR EVENT ASSESSMENT AND FOLLOW-UP

Subjects with AEs will be followed-up until the event is resolved or until, in the opinion of the investigator, the event is stabilized or determined to be chronic. Details of AE resolution must be documented in the source documents.

Subjects should be followed up for 30 days after receiving the last dose of study drug, and any AEs that occur during this time should be reported according to the procedures outlined above.

8.2.4.1 DOCUMENTATION AND REPORTING OF ADVERSE EVENTS

AEs should be reported and documented in accordance with the procedures outlined below. All AEs occurring during the study must be documented on the relevant source pages. The following data should be documented for each AE:

- Description of the symptom event
- Classification of ‘serious’ or ‘not serious’
- Severity
- Date of first occurrence and date of resolution (if applicable)
- Action taken
- Causal relationship
- Outcome of event (unknown, recovered, not yet recovered, recovered with sequelae, death [with date and cause reported])

8.2.5 REPORTING EVENTS TO PARTICIPANTS

When necessary for the safety and proper treatment of the patient, the investigator can unmask the patient’s treatment assignment to all site personnel to determine which treatment has been assigned and institute appropriate follow-up care.

The reason for unmasking the patient must be recorded in the patient’s source documents.

A report of the results of this study may be published, sent to the appropriate health authorities in any country in which the study drug may ultimately be marketed, and published in part as required by appropriate health authorities (e.g., Clinical Trials posting and disclosure), but the patient’s name will not be disclosed in these documents.

Patients will be informed that the study is posted and the results eventually disclosed by appropriate health authorities (e.g., Clinical Trials posting or freedom of information by the FDA).

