3 OBJECTIVES AND ENDPOINTS

Table 3-1 Table of Objectives, Endpoint, and Endpoint Justification

| OBJECTIVES | ENDPOINTS | JUSTIFICATION FOR ENDPOINTS |
|---|---|---|
| To evaluate the safety and tolerability of AZR-MD-001 1.0% ointment/semi-solid drug applied to the lower lid twice-weekly following evening only dosing for up to 3 months in MGD. To evaluate whether dosing Hylo-Forte® approximately 5 minutes before study ointment will enhance either the safety or tolerability of AZR-MD-001 1.0% following evening only dosing. | Safety/Adverse Events: 
Incidence rates of each treatment-emergent adverse events.Tables for all treatment-emergent adverse events regardless of causality.Tables for all treatment-emergent adverse events considered to be treatment-related.Shift tables for safety variables (e.g., IOP, biomicroscopy, and ophthalmoscopy). | The endpoints for safety and tolerability are all commonly used in ophthalmic drug and device trials. |

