4 STUDY DESIGN

4.1 OVERALL DESIGN

Single-center, single-masked (the individual(s) performing efficacy and safety measures will be masked to treatment assignment for the patient(s) they are assessing), vehicle-controlled, randomized, parallel group study. For all dose groups a screening visit will be followed by a baseline visit 14 days later (qualification period). At the end of the qualification period patients who still exhibit signs of MGD and who can comply with dosing instructions at the baseline visit will be enrolled into a 3-month treatment period.. At the baseline (Day 0) visit, patients will be randomly assigned in a 2:2:1:1 ratio to receive either AZR-MD-001 1.0% ointment/semi-solid drug or AZR-MD-001 1.0% ointment/semi-solid drug plus Hylo-Forte® or AZR-MD-001 vehicle or AZR-MD-001 vehicle plus Hylo-Forte® for twice-weekly evening administration for 3 months. Where applicable, Hylo-Forte® will be dosed approximately 5 minutes before study ointment. The study flow is shown in Figure 1.

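### Section 8.2.5 lets a safety code break be disclosed to the whole site, with no need-to-know limit and no exemption for the masked assessors

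*Combined protocol and SAP*

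**What the plan says.** Sections 1.2 and 4.1 describe a single-masked study in which "the individual(s) performing efficacy and safety measures will be masked to treatment assignment for the patient(s) they are assessing". Section 6.2 gives that commitment a duration: "Site personnel conducting efficacy and safety measures will be masked to the treatment assignment for the 3 month treatment period". It supports it with a separation of duties: "The individual dispensing drug and monitoring compliance will not be the same person who conducts efficacy or safety measures for a given patient".

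Section 8.2.5 covers breaking the code. The condition is "When necessary for the safety and proper treatment of the patient". When it is met, the investigator is allowed, though not obliged, to unmask that patient's "treatment assignment to all site personnel to determine which treatment has been assigned and institute appropriate follow-up care". The one safeguard attached is documentary: "The reason for unmasking the patient must be recorded in the patient’s source documents".

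The study's objectives are safety and tolerability. The endpoints in section 3 include "Tables for all treatment-emergent adverse events considered to be treatment-related", and shift tables for variables such as IOP, biomicroscopy and ophthalmoscopy.

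**The concern.** Assessor masking is the only masking that the design section claims. Section 8.2.5 allows it to be given up for a patient, site-wide, at the moment a safety problem arises. Disclosure that serves the patient's care and disclosure to everyone at the site are different things, and the section does not separate them.

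What is at stake is assessment bias in the safety data. The trigger is tied to safety and care, so any loss of masking does not fall on patients at random. It falls on patients whose clinical course made the assignment worth knowing, in a trial whose conclusions are about safety. An assessor who knows the treatment may grade later findings differently, and the plan provides no way to identify which findings those are.

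**Working it through.** The plan gives no figure on this point. The sample size is described as empirical (section 9.1) and no number of code breaks is anticipated, so there is nothing to reproduce. The check is mainly a comparison of the sections.

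1. **Are assessors among those who may be told?** Yes. Section 6.2 calls the people doing the measures site personnel, and section 8.2.5 uses the same term with no exception.

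2. **Does any other text narrow the disclosure or deal with its consequences?** None was found. Section 8.2.5 asks only for the reason. The documents do not require a record of who was told or when, a substitute masked assessor, or that severity and causality be rated before the code is opened. Sections 9.2 and 9.4 do not say how data recorded after a code break are flagged or analysed.

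3. **Does assessment continue after a code break?** It can. Section 8.2.4 has adverse events followed until they resolve, stabilise or are judged chronic. Section 7.1 asks that exit procedures be attempted after early discontinuation, and it does not list unmasking as a reason to discontinue. In the Schedule of Activities, slit-lamp biomicroscopy is done at every visit. Ophthalmoscopy and IOP are scheduled only at screening and at Month 3 (exit). For a patient unmasked before exit, the only scheduled post-treatment ophthalmoscopy, which supplies that patient's entry in the shift table, would therefore come after the code break.

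4. **Which data depend on the masked person's judgement?** Biomicroscopy and ophthalmoscopy findings, and other graded measures such as staining. Severity (8.2.3.1) and causality (8.2.3.2) are also judgements, but those sections do not name the rater. Section 8.2.1 makes the investigator responsible for documenting adverse events.

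5. **Scale of one patient.** Inputs: about 30 patients randomized (section 5.5) at 2:2:1:1 (section 4.1).
   - Arm size = 30 × ratio ÷ 6. Active arms: 30 × 2 ÷ 6 = 10 each. Vehicle arms: 30 × 1 ÷ 6 = 5 each.
   - Shift in incidence if one patient is classified differently = 100 ÷ n. Active arm: 100 ÷ 10 = 10 percentage points. Vehicle arm: 100 ÷ 5 = 20 points.
   - With arms pooled: active 100 ÷ 20 = 5 points; vehicle 100 ÷ 10 = 10 points.

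These figures show how much one altered classification weighs. They do not say how often one would occur, so a total bias cannot be computed.

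**The case against.** Several points on the other side are sound.

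- **It is an exception, not a contradiction.** A reader might infer that 8.2.5 flatly contradicts 6.2, or that every code break goes to the whole site. The documents do not support that. The provision is conditional on clinical need, and the verb is permissive. A general masking rule with an emergency exception is normal; what is missing is a limit on the exception.

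- **Code breaks need not coincide with the important events.** A reader might infer that the unmasked patients are precisely those with the most important adverse events. The trigger is that knowing the assignment is needed for care, which is not the same as severity or seriousness. Section 4.2 says the sister study's findings reversed when treatment was stopped, and section 8.2.3.3 lists stopping study drug as an action; neither makes a code break part of managing an event. Some ratings may also have been recorded before the code was opened.

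- **The sister study gives no rate.** A reader might take its three discontinuations for adverse events as a guide to the number of code breaks here. The text reports no unmasking, no arms and no denominator for those three, and the population had contact lens discomfort. No percentage can be drawn from it.

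- **Limiting disclosure does not protect every rating.** If the treating investigator rates causality, that rater knows the assignment after a code break under any rule. Section 6.2 separates the dispenser from the assessor, but not the treating clinician from the assessor; at a single site they may be the same person.

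- **Other routes to knowledge of treatment exist.** Patients are not stated to be masked in the design section (although section 6.1.3 refers to a double-masked period), and section 6.1.1 describes an orange active ointment and a white vehicle. Patient-reported outcomes are exposed to this in every patient, so a rare code break may add little there. Assessor-graded findings are different: section 6.2 is written to protect them.

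- **Some traceability exists.** The reason for unmasking is recorded and individual data are listed (section 9.4.6). That does not show who was told, when, or which values followed.

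These points narrow the concern. They leave the absence of a need-to-know limit and of an assessor exemption untouched.

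**Conclusion.** The point holds in a limited form. Section 8.2.5 permits, but does not require, disclosure of a patient's assignment to everyone at the site, including the staff whom section 6.2 undertakes to keep masked. Later graded safety measures in such a patient could then be made with knowledge of treatment. This is an avoidable source of assessment bias in the one layer of masking that the design section claims.

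Its total size is unknown because the documents give no basis for the number of code breaks. The per-patient weight is 10 or 20 percentage points in a single arm, or 5 or 10 with arms pooled. This assumes that about 30 patients split as 10, 10, 5 and 5, and that a classification actually changes. The wording gap is certain; its practical effect depends on how often the code is opened and on whether the investigator uses the full permission. It should be corrected, but it does not by itself undermine the trial.

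**What to change.** In section 8.2.5:

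- Replace the site-wide disclosure with disclosure to the treating investigator and only those others who need the assignment for the patient's care.
- State that staff performing efficacy and safety measures stay masked where they are not also treating the patient.
- Ask that severity and causality be recorded before the code is opened, where feasible and without delaying care.
- Log the date of the code break and the persons told, in addition to the reason.

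In section 9.4.6, flag assessments made after unmasking in the individual listings.

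The investigator's access to the code for patient care is unchanged. The cost is one or two sentences, a log entry and a listing flag. Where the treating clinician is also the assessor, that patient's later data are flagged as unmasked and no extra assessor is required. In that case the change makes the loss of masking visible but does not prevent it.
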